8.7.2 Safety Interim Analyses

[figure not shown]
As noted in Section 7.3.2 – Data Monitoring Committee, the eDMC will be responsible for periodic interim safety reviews as specified in the DMC charter.

8.8 Multiplicity

The multiplicity strategy specified in this section will be applied to the primary hypothesis (superiority of pembrolizumab to placebo in OS) and the secondary hypotheses of superiority of pembrolizumab in PFS or ORR.

The overall Type-I error across the testing of the OS, PFS, and ORR hypotheses is strongly controlled at α =2.5% (one-sided). The multiplicity strategy will follow the graphical approach of Mauer and Bretz [58]. Figure 3 provides the multiplicity strategy diagram of the study.

Product: MK-3475 **Protocol/Amendment No.:** 394-06

Multiplicity Strategy Figure 3

In the diagram shown in Figure 3, when a particular null hypothesis is rejected, the arrows leading to it are removed, and the Type I error allocated to the null hypothesis that was rejected are re-distributed to other hypotheses. The arrows on the diagram show how the Type I error allocated to a hypothesis that was successfully tested will be re-distributed. Initially, $\alpha=2.3\%$ (23/25 of the overall total $\alpha=2.5\%$ for testing the OS, PFS and ORR) is allocated to the OS hypothesis and α =0.2% is allocated to the PFS hypothesis.

In detail, if PFS and OS hypotheses are both rejected on the initial alpha, then ORR hypothesis will be tested on the 2.5% alpha level. If PFS hypothesis is rejected on the initial alpha level 0.2% while OS is NOT rejected on the initial alpha 2.3%, then ORR hypothesis will be tested on the 0.2% alpha level. If ORR hypothesis can be rejected on the 0.2% alpha level, then OS hypothesis will be retested on the 2.5% alpha level. If PFS hypothesis is NOT rejected on the initial alpha level 0.2% but OS hypothesis is rejected on the initial alpha 2.3%, then PFS hypothesis can be re-tested on the 1.35% alpha level and ORR hypothesis can be tested on the 1.15% level. After that, we will follow the same procedure of hypothesis testing and type-I error re-distribution as illustrated in Figure 3.

OS hypothesis: The OS hypothesis will be tested following a group sequential approach. The testing of the OS hypothesis will be based on an OS test statistic calculated from study data at the first interim analysis. If unsuccessful at the first IA, the OS hypothesis will be tested at the second interim analysis time and, if unsuccessful at the second IA, the OS hypothesis will be tested at the final analysis time. No futility test is planned at the interim analyses. The nominal Type I error rates for the two interim analyses and final analysis that will allow tight control of the overall Type I error for testing the OS hypothesis will be derived using the alpha-spending function approach based on the overall Type I error allocated to the OS hypothesis. The group sequential testing of the OS hypothesis will be conducted with efficacy boundaries (superiority test only). The OS efficacy boundary will be set using the Lan-DeMets spending function that approximates an O'Brien-Fleming boundary. The OS hypothesis will initially be tested at the overall Type I error α =2.3%. If both the PFS and ORR null hypotheses have been rejected at the α =0.2% level, the OS hypothesis will be tested at Type I error level of $\alpha=2.5\%$.

Table 15 summarizes the timing, sample size and decision guidance of the interim analyses and final OS analysis. Interim analysis spending for OS analyses will be based on the expectation of 345 OS events at the final analysis and the final analysis spending will be updated based on spending alpha using the actual number of OS events at times of analysis using spending functions as noted above.

Table 15 Summary of Timing, Sample Size and Decision Guidance for the Interim Analyses and Final Analysis of Overall Survival

		Study				Efficacy Boundary Crossing		crossing [†]
Type I Error		Calendar			Information	Nominal	Hazard	
(Overall α)	Analysis	Time	N§	Events	Fraction	α	Ratio	Power
	IA1	Month 17	225	100	0.30	<0.01%	~0.42	0.9%
2.3%	IA2	Month 31	450	276	0.80	1.10%	~0.75	70%
	Final	Month 37	450	345	1.00	1.98%	~0.79	87%
	IA1	Month 17	225	100	0.30	<0.01%	~0.43	1.1%
2.5%	IA2	Month 31	450	276	0.80	1.22%	~0.75	72%
	Final	Month 37	450	345	1.00	2.14%	~0.79	88%

[†] Based on Lan-DeMets spending function that approximates an O'Brien-Fleming boundary.

PFS hypothesis: The PFS hypothesis will be tested following a group sequential approach. The testing of the PFS hypothesis will be at the first interim analysis time. If unsuccessful at the first IA, the PFS hypothesis will be tested at the second interim analysis time, and this will be final analysis for PFS. No futility test is planned at this interim analysis. The primary testing of the PFS hypothesis will initially be tested at one-sided Type I error α =0.2%. Depending on the results of testing of the OS and ORR hypothesis, the PFS hypothesis can be tested at a one-sided Type I error level of α =1.35% or α =2.5%. At the second interim analysis, it is expected that approximately 395 PFS events would have been accumulated assuming 1) a hazard ratio of 0.65; 2) Progression-free survival follows an exponential distribution with a median of 1.5 months in the control arm; 3) an enrollment time of 31 months with a recruitment rate of 16 subjects per month and a 6-month ramp up time, and 4) a monthly drop-out rate of ~1%. The corresponding power is expected to be over 88% when testing at a Type I error α =0.2%.

Table 16 summarizes the timing, sample size and decision guidance of the interim and final PFS analyses. Interim analysis spending for PFS analysis will be based on the expectation of 395 PFS events at the final analysis and the final analysis spending will be updated on spending alpha using the actual number of PFS events at times of analysis when the criteria for triggering the final PFS analysis is complete.

[§] Expected number of subjects randomized into the study at the time of analysis.

Protocol/Amendment No.: 394-06

Table 16 Summary of Timing, Sample Size and Decision Guidance for the Interim Analysis and Final Analysis of Progression Free Survival

		Study Efficacy Box		Boundary C	rossing†			
Type I Error		Calendar			Information	Nominal	Hazard	
(Overall α)	Analysis	Time	N§	Events	Fraction	α	Ratio	Power
0.2%	IA	Month 17	225	174	0.44	<0.01%	~0.48	3.4%
0.276	FA	Month 31	450	395	1.00	0.2%	~0.74	88%
1.250/	IA	Month 17	225	174	0.44	0.02%	~0.57	20%
1.35%	FA	Month 31	450	395	1.00	1.34%	~0.79	97%
2.50/	IA	Month 17	225	174	0.44	0.07%	~0.60	31%
2.5%	FA	Month 31	450	395	1.00	2.5%	~0.81	98%

[†] Based on Lan-DeMets spending function that approximates an O'Brien-Fleming boundary.

ORR hypothesis: ORR by treatment group will be estimated at each interim analysis and the final analysis. The initial alpha allocated to ORR is zero. If PFS or OS null hypothesis is rejected, depending on the results of testing of the OS and PFS hypothesis, the ORR hypothesis can be tested at a one-sided Type I error level of $\alpha = 0.2\%$, $\alpha = 1.15\%$, or $\alpha = 2.5\%$. The ORR hypothesis will be tested following a group sequential approach. The testing of the ORR hypotheses will be at the first interim analysis time. If unsuccessful at the first IA, the ORR hypotheses will be tested at the second interim analysis time, and, if unsuccessful, at the final analysis time. Subjects who will be included in the ORR analysis are those who have "mature ORR information", defined as subjects who were enrolled at least 24 weeks prior to the interim data cutoff dates and thus had an opportunity to have at least 4 scheduled scans if not discontinued. For the first interim analysis, 163 subjects with at least 24 weeks follow up will be included for ORR analysis and information fraction is expected to be about 0.36. It is projected that there will be approximately 362 such subjects at the second interim analysis time point and the information fraction is expected to be about 0.80 (362 with "mature ORR information" of 450 enrolled). The nominal Type I error rates for the interim analyses and final analysis that will allow tight control of the overall Type I error for testing the ORR hypothesis will be derived using the alpha-spending function approach. The group sequential testing of the ORR hypothesis will be conducted with an efficacy boundary only. The efficacy boundary for the ORR will be set using an Exponential spending function $f(t) = \alpha^{t^{-v}}$ [62] with parameter v=0.25, which yields a Pocock-like boundary. The ORR hypothesis is initially allocated a Type I error α =0% and thus, cannot be tested unless one or both of the PFS or OS null hypotheses have been rejected. Depending on the results of the OS and PFS hypotheses testing, the ORR hypothesis can be tested at Type I error levels of α =0.2%, 1.15%, or 2.5%.

Table 17 shows the boundary thresholds corresponding to a group sequential testing of the ORR hypothesis at each of these Type I error levels. The interim analysis information fractions will be adjusted according to the proportion of the total number of subjects actually randomized (which will be known at the time of the interim analyses) who were enrolled at least 24 weeks prior to the interim data cutoff dates and thus had an opportunity to have at least 4 scheduled scans if not discontinued by the time of interim analysis. The Exponential spending function will then be used to update the boundary thresholds in Table 17.

03-Nov-2022

[§] Expected number of subjects randomized into the study at the time of analysis.

Protocol/Amendment No.: 394-06

Table 17 Efficacy Boundaries for Testing the ORR Hypothesis

Type I Error		Study		Information	Efficacy	Boundary Cro	ossing [†]
(Overall α)	Analysis	Calendar Time	N^{\ddagger}	Fraction	Nominal α	ORR Δ§	Power
	IA1	Month 17	163	0.36	0.03%	~16.77%	17%
0.2%	IA2	Month 31	362	0.80	0.12%	~10.05%	73%
	Final	Month 37	450	1.00	0.11%	~9.07%	85%
	IA1	Month 17	163	0.36	0.31%	~12.95%	42%
1.15%	IA2	Month 31	362	0.80	0.67%	~7.85%	91%
	Final	Month 37	450	1.00	0.58%	~7.18%	96%
	IA1	Month 17	163	0.36	0.86%	~11.09%	58%
2.50%	IA2	Month 31	362	0.80	1.45%	~6.80%	96%
	Final	Month 37	450	1.00	1.23%	~6.28%	98%

 $^{^{\}dagger}$ Based on Exponential (v=0.25) spending function. ORR is tested for superiority only.

The spending function planned to be used for the testing of the OS and ORR hypotheses satisfy the requirements laid out in Maurer and Bretz [58]. More details will be included in the sSAP.

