8.6.1.3 Objective Response Rate (ORR)

Stratified Miettinen and Nurminen's method [57] with weights proportional to the stratum size will be used for the comparison of the objective response rates between the treatment arms. A 95% confidence interval for the difference in response rates between the pembrolizumab arm and the control arm will be provided. The stratification factors and strata applied to the analysis will be the same as those factors and strata used in the stratified analysis for overall survival.

The ORR analysis will be conducted according to the hypotheses testing plan as described in Section 8.7 Interim Analyses and Section 8.8 Multiplicity.

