8.7.1 Efficacy Interim Analyses

Two interim analyses and one final analysis are planned in this trial. The timing and the purpose of each analysis are summarized in Table 14. A detailed description of the multiplicity adjustment and hypotheses testing plan is provided in Section 8.8 Multiplicity.

The first interim analysis will be performed at approximately Month 17, at which time the first 163 randomized subjects have at least 24 weeks follow-up. The main purpose of this interim analysis is to conduct the analysis for ORR on the first 163 randomized subjects, evaluate the consistency of efficacy and safety in this study to the reference global data, and to conduct an interim testing for efficacy on the PFS and OS endpoints for all the subjects randomized at that time (superiority only). Consistency of efficacy will be evaluated by comparing the treatment effect observed in this study to the reference global data (based on point estimates). Approximately 225 subjects will be enrolled at the first interim analysis cutoff, with approximately 174 PFS events and 100 OS events projected to be accumulated. The main purpose of the second interim analysis is to conduct the primary testing for efficacy on the PFS hypothesis and to conduct an interim testing for efficacy on the OS hypothesis (superiority only). It will be performed when enrollment is complete and approximately 276 OS events (~80% of the target 345 total OS events) are observed. It is projected that this event count will be accumulated at approximately 31 months after the start of the study. Approximately 395 PFS events are expected to be accumulated by then. Under assumptions specified in Section 8.9 sample size and power calculation, at the time of the secondary interim analysis: 1) a total of approximately 395 PFS events for testing the PFS hypothesis at Type I error α=0.2% provides approximately 88% power to successfully demonstrate the PFS hypothesis; and 2) a total of approximately 276 OS events for testing the OS hypothesis at Type I error α =1.10% provides approximately 70% power to successfully demonstrate the OS hypothesis.

If superiority of PFS or OS (pembrolizumab vs. placebo) is demonstrated at one of the interim analyses, the ORR hypothesis will be tested according to the group-sequential boundaries for ORR analysis (see Table 17 in Section 8.8 Multiplicity).

The final analysis (FA) will be performed when approximately 345 OS events are observed which is expected at Month 37.

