Protocol/Amendment No.: 394-06

Table 14 Summary of Interim and Final Analyses Strategy

Analysis	Endpoint(s)	Criteria for Conduct of Analysis	Estimated Time after First Subject Randomized	Primary Purpose of Analysis
IA 1	ORR, DOR, PFS, OS	First 163 randomized subjects have at least 24 weeks follow-up	~17 months	Descriptive ORR analysis, consistency evaluation
IA 2	ORR, PFS, OS	~276 OS events observed	~31 months	PFS FA OS IA
FA	OS, ORR	~345 OS events observed	~37 months	OS FA

Abbreviations: FA = final analysis; IA = interim analysis; PFS = progression-free survival; ORR = overall response rate; OS = overall survival

The eDMC will serve as the primary reviewer of the unblinded results of the interim analyses and will make recommendations. Depending on the recommendation of the eDMC, the Sponsor may prepare a regulatory submission. NOTE: no futility test is planned in the interim analysis.

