8.9 Sample Size and Power Calculations

The study will randomize subjects in a 2:1 ratio into the pembrolizumab plus BSC arm and the control arm (placebo plus BSC).

The final analysis is event driven (i.e., the testing of the OS and PFS hypotheses will be conducted upon accumulation of a preset number of events). The study is designed and will be conducted to accumulate approximately 345 OS events unless superiority in OS is proven at the interim analyses.

OS Analysis: A total of approximately 345 OS events are required to test the OS hypothesis at Type I error rate of α =2.3% with ~87% power (see Table 15) if the underlying OS hazard ratio (pembrolizumab/control) is 0.7. A total of approximately 450 subjects are needed to be enrolled into the study in order to accumulate approximately 345 OS events at approximately Month 37 after study start.

The sample size and power calculation is based on the following assumptions: 1) a hazard ratio of 0.7; 2) overall survival follows an exponential distribution with a median of 6.0 months in the control arm; 3) an enrollment rate of 16 subjects per month with a 6-month ramp up time; and 4) a monthly dropout rate of $\sim 0.2\%$.

PFS Analysis: As described in Section 8.7 Interim Analysis, the primary PFS analysis will be conducted at the same time as the OS interim analysis at approximately Month 31 after

[‡] Expected number of subjects who were enrolled at least 24 weeks prior to the data cutoff date and thus had an opportunity to have at least 4 scheduled scans at the time of ORR analysis.

 $^{^{\}S}\Delta$ = ORR in pembrolizumab group - ORR in control group. The assumed expected ORR in pembrolizumab and control groups are 15% and 3%, respectively.

study start. It is projected that approximately 395 PFS events will be accumulated at this time. With 395 PFS events, the testing of the PFS hypothesis at Type I error α =0.2% has approximately 88% power to demonstrate that pembrolizumab is superior to the control with respect to PFS if the underlying PFS hazard ratio (pembrolizumab/control) is 0.65.

The sample size and power calculation is based on the following assumptions: 1) a hazard ratio of 0.65; 2) progression-free survival follows an exponential distribution with a median of 1.5 months in the control arm; 3) an enrollment rate of 16 subjects per month with a 6-month ramp up time; and 4) a monthly dropout rate of $\sim 1\%$.

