The sample size and power calculation were performed in the software EAST and R (package "gsDesign").

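### IA1 rows of the decision tables: the printed ORR power and differences do not describe the planned test at 163 subjects, and 163 mature subjects do not fit Month 17 with 225 enrolled

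*Protocol*

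**What the plan says.** On the ORR boundaries, protocol Section 8.8 states: "Table 17 shows the boundary thresholds corresponding to a group sequential testing of the ORR hypothesis at each of these Type I error levels". Protocol Table 17 and SAP Table 9 give the same IA1 rows for ORR: 163 subjects, information fraction 0.36, nominal alpha 0.03/0.31/0.86%, differences of about 16.77/12.95/11.09 points and power 17/42/58%, at overall alpha 0.2/1.15/2.5%. The Table 17 footnote states: "The assumed expected ORR in pembrolizumab and control groups are 15% and 3%, respectively". Protocol Section 8.6.1.3 plans a stratified Miettinen-Nurminen test in which "weights proportional to the stratum size will be used for the comparison of the objective response rates". Section 8.9 adds: "The sample size and power calculation were performed in the software EAST and R".

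Section 8.7.1 sets IA1 at about Month 17, "at which time the first 163 randomized subjects have at least 24 weeks follow-up", with about 225 enrolled, 174 PFS events and 100 OS events. Accrual is 16 per month after a 6-month ramp-up.

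Three statements limit the weight of the IA1 ORR row. On alpha: "The initial alpha allocated to ORR is zero". Table 14 gives the primary purpose of IA1 as "Descriptive ORR analysis, consistency evaluation". On updating, the protocol says: "The Exponential spending function will then be used to update the boundary thresholds in Table 17".

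**The concern.** With 54 control subjects and a 3% response rate, fewer than two control responses are expected. A normal approximation is weak there, especially at nominal alphas well below 1%. If the printed power is too high and the printed differences too small, the eDMC could see an observed difference at or above the tabulated one and expect a crossing that the planned test does not give.

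Separately, 163 of 225 subjects with 24 weeks of follow-up implies a much slower recent accrual than the plan assumes. In that case the IA1 rows for OS, PFS and ORR do not all describe the same data cut.

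**Working it through.** **(a) ORR at IA1**

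Inputs: 163 subjects at 2:1 (109 versus 54), rates 15% and 3%, overall alphas 0.2/1.15/2.5% one-sided, spending function f(t) = alpha^(t^-0.25).

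1. *Nominal alpha.* With t = 163/450 = 0.362, f(t) = 0.033/0.316/0.861% and z = 3.404/2.730/2.382. These agree with the tables.

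2. *Reproducing the printed power.* Printed difference divided by z gives an implied standard error of 4.93/4.74/4.66 points. Then Φ(12/SE − z) = 16.6/42.1/57.7%, which is the printed 17/42/58%. Neither standard error of the comparison has these values:
 - Null, pooled rate (2×15+3)/3 = 11%: √(0.11×0.89×(1/108.67+1/54.33)) = 5.20 points.
 - Alternative: √(0.15×0.85/108.67+0.03×0.97/54.33) = 4.13 points.

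 Weighting the two by the z-values for alpha and power of the whole design gives 4.92/4.73/4.65. So the rows come from a normal approximation set at the final 450 subjects and scaled down to 163.

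3. *The planned test.* For a zero difference the Miettinen-Nurminen statistic is z = d / √(p̄(1−p̄)(1/n1+1/n0)·N/(N−1)), with p̄ the pooled observed rate, so the standard error grows with d. At a 3% control rate and d = 16.77, p̄ = 0.03 + (109/163)×0.1677 = 0.142, SE = 5.83, z = 2.88 and p = 0.20%. The other two printed differences give p = 0.78% and 1.48%. Nominal alphas are 0.03/0.31/0.86%.

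4. *Exact enumeration, 109 versus 54:*

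| Overall alpha | Printed power | Exact, control 3% | Control 2% | Control 4% | Printed difference | Needed at 3% control |
|---|---|---|---|---|---|---|
| 0.2% | 17% | 3.2% | 5.2% | 2.0% | 16.77 | 21.55 |
| 1.15% | 42% | 29.4% | 41.5% | 20.5% | 12.95 | 15.52 |
| 2.5% | 58% | 48.9% | 63.2% | 36.8% | 11.09 | 12.68 |

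5. *Smallest crossing result by control responders* (responders of 109, difference in points):

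| Control responders of 54 (probability at 3%) | alpha 0.2% | alpha 1.15% | alpha 2.5% |
|---|---|---|---|
| 0 (19%) | 21, 19.3 | 14, 12.8 | 11, 10.1 |
| 1 (32%) | 25, 21.1 | 18, 14.7 | 15, 11.9 |
| 2 (26%) | 29, 22.9 | 22, 16.5 | 19, 13.7 |
| 3 (14%) | 32, 23.8 | 25, 17.4 | 22, 14.6 |

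 A difference of 16.77 is too small for every control count from 0 to 5. The values 12.95 and 11.09 suffice only with 0. In the 2.5% row with 1 control responder the shortfall is harmless: the attainable differences on either side of 11.09 are 14/109 − 1/54 = 10.99 and 15/109 − 1/54 = 11.91, and the latter crosses.

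6. *Stratified test.* Simulated with five strata, power is about 3/26–27/46–48%. The stratum shares are assumed, since the documents do not give them.

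7. *Later looks.* Simulated cumulative power is 74/91/96% at IA2 (printed 73/91/96%) and 88/97/99% at the protocol's final analysis (printed 85/96/98%). For the SAP's two-look design it is 90/98/99% at the final (printed 88/97/99%). The overstatement is confined to IA1.

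**(b) Timing of IA1**

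1. 24 weeks = 5.52 months, and 5.52 × 16 = 88 subjects. At Month 17 this window starts at Month 11.48, after the ramp has ended, so its shape does not matter. The protocol's own IA2 projection uses the same gap: 450 − 362 = 88.
2. At IA1, 225 − 88 = 137, not 163. A gap of 225 − 163 = 62 would need 62/5.52 = 11.2 per month.
3. With a linear ramp from 0 to 16 (48 subjects by Month 6), N(17) = 48 + 11×16 = 224, with about 98 OS and 174 PFS events. All three fit the printed figures. Mature subjects number 48 + 5.48×16 = 136.
4. The 163rd subject enrols at 6 + 115/16 = Month 13.19. That subject has 16.6 weeks at Month 17 and reaches 24 weeks at Month 18.71, when N is about 251 with about 117 OS events (fraction 0.34, printed 0.30) and 200 PFS events (0.51, printed 0.44).
5. At that later cut, the OS boundary hazard ratio is about 0.48/0.49 with power 2.8/3.2% at alpha 2.3/2.5% (printed 0.42/0.43 and 0.9/1.1%). For PFS at alpha 0.2/1.35/2.5% they are about 0.53/0.61/0.64 and 9/34/47% (printed 0.48/0.57/0.60 and 3.4/20/31%).

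**The case against.** The strongest reply is that the printed ORR figures are not slips. They are the output of a standard normal approximation, the kind the named software gives, and are marked as approximate. The nominal alphas beside them are correct. This is true, and it explains the source. It does not make the IA1 power right for the test that will be run.

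A second reply is that no single difference can be right. A 3% rate among 54 is 1.62 responders, which cannot occur. With 2 control responders, 28/21/18 treated responders meet 21.55/15.52/12.68, but the test needs 29/22/19. With 0 or 1, the replacement values are stricter than necessary. This stands: any tabulated difference must be labelled with its control rate and must not serve as the decision rule. Power is also sensitive: at a 2% control rate the exact values reach 42% and 63%, so only the 0.2% row is far off under every control rate tried.

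Third, the consequence is small. Under the design rates, the chance of meeting the printed difference without rejecting is 8.1/10.3/8.6%. It matters only if PFS or OS is rejected at IA1, which happens in about 3–4% of trials at Month 17 or 9–12% at the later cut. I agree.

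On timing, the trigger is 163 subjects with 24 weeks, Month 17 and 225 are approximate, and ORR boundaries are updated to actual enrolment. So no decision rests on Month 17, but the projections still contradict each other. The replacement dates depend on the ramp: monthly steps give 232 enrolled, 144 mature and Month 18.2, and a later-starting step gives 216, 128 and Month 19.2. None yields 163. The SAP also records that all subjects had 24 weeks by IA2, so actual accrual had already departed from the projection.

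**Conclusion.** Both parts hold, at minor severity. The IA1 ORR power is overstated by about 14, 13 and 9 percentage points at overall alpha 0.2/1.15/2.5%, and the printed differences are about 4.8, 2.6 and 1.6 points too small at a 3% control rate. The number of mature subjects at Month 17 is about 136 rather than 163. Month 17, 225 enrolled and the OS and PFS event counts agree with one another; only the 163 does not fit.

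Type I error, alpha allocation and sample size are unaffected. OS and PFS power at IA2 and final is essentially unchanged, and IA2 ORR power is right as printed. The result rests on the stated 15% and 3% rates, a 109/54 split, an unstratified calculation (stratified slightly lower) and, for the dates and event counts, a linear ramp.

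**What to change.** In the IA1 rows of protocol Table 17 and SAP Table 9, print power of about 3/29/49%, labelled unstratified and slightly lower with five strata, and differences of 21.55/15.52/12.68 points, labelled as applying at a 3% control rate. Add a footnote that the difference needed depends on the control rate and that the nominal alpha is the decision rule; listing the smallest crossing result by number of control responders would make this usable. IA2 power needs no change. Final power at alpha 0.2% may be raised to about 88% (protocol) and 90% (SAP). The final differences are slightly conservative and may stay.

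Reconcile 163, 225 and Month 17; which side to change is the sponsor's choice.
- If the 163-subject trigger stays, restate IA1 as about Month 18.7, N about 251, about 117 OS and 200 PFS events, with the OS and PFS boundaries and power given above.
- If Month 17 and 225 stay, use about 136 mature subjects: ORR fraction 0.30, nominal alpha 0.023/0.242/0.691%, exact power about 0.5/13–14/31–35%, and differences of about 25.8/18.7/15.3 points at a 3% control rate.

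The cost is a few table cells, one footnote and one projection, with no change to alpha allocation, sample size or method. If IA1 has already been held, a footnote to the tables is enough.
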